4.1. Overall Design

This study will be a Phase 1b, 2-part, multi-center, open-label, fixed-sequence drug interaction study in 40 male and female participants who have been diagnosed with migraine for at least 1 year and are aged 18 through 50 years. In Part 1, 20 participants will receive a single oral dose of 100 mg ubrogепant alone (Study Intervention A) on Day 1, a single SC injection of 140 mg erenumab alone (Study Intervention B) on Day 8, followed by once daily oral doses of 100 mg ubrogепant on Days 12 through 15 (Study Intervention D) under fasted conditions. Similarly, in Part 2, a separate cohort of 20 participants will receive a single oral dose of 100 mg ubrogепant alone (Study intervention A) on Day 1, 2 consecutive SC injections of 120 mg galcanezumab alone (Study intervention C) on Day 8, followed by once daily oral doses of 100 mg ubrogепant on Days 12 through 15 (Study Intervention D) under fasted conditions.

If all doses are well tolerated, the duration of participation in the study will be 46 ± 3 days (Day -1 through the safety Follow-up Visit on Day 45), not including the Screening Visit.

- Duration:
 - Screening: Up to 21 days (Day -21 to Day -1)
 - Intervention Period: Up to a total of 17 days (Day -1 to Day 16)
 - Follow-up period: 30 (± 3) days after the last dose

- PK and Biomarker Sampling

In Part 1 and Part 2, PK blood samples for the analysis of ubrogепant and CGRP concentrations will be collected at 0 hour (predose), 0.5, 1, 1.5, 2, 3, 4, 5, 6, 8, 12, 14, and 24 hours postdose on Days 1 and 12.

[REDACTED]

- Safety Measurements

The safety and tolerability profiles when ubrogепant and erenumab or ubrogепant and galcanezumab are co-administered and when each study intervention is administered alone in participants with migraine will be evaluated by clinical assessment of AEs, physical examinations, safety 12-lead ECGs, standard laboratory safety tests (hematology, serum chemistry, and urinalysis), and by measurements of vital signs at specified time points after each study intervention.

- Number of Participants

A total of 40 participants at up to 3 sites in the United States will be enrolled in the study; 20 participants in Part 1 and a separate cohort of 20 participants in Part 2. Part 1 and Part 2 will enroll in parallel. [REDACTED]

██████████. Participants who prematurely discontinue from the study may be replaced at the discretion of the sponsor.

4.2. Scientific Rationale for Study Design

The multi-center, open-label, fixed-sequence design is considered adequate to assess the potential effect on the safety and PK of ubrogепant when ubrogепant and erenumab or ubrogепant and galcanezumab are co-administered. Considering the long half lives of erenumab and galcanezumab (about 28 days), the fixed-sequence design allows for the evaluation of the effect of erenumab/galcanezumab on the PK of ubrogепant. The washout period of 7 days between Study Intervention A and Study Intervention B (Part 1) or Study Intervention C (Part 2) is adequate given ubrogепant's short $T_{1/2}$ of 5-7 hours. ██████████

██████████ Multiple dose administration of ubrogепant following erenumab or galcanezumab administration will help to assess the safety/tolerability of the combinations in a potential real world setting of administering ubrogепant to acutely treat an acute migraine attack in participants who are already on a preventive medication, either erenumab or galcanezumab.

4.3. Justification for Dose

- The ubrogепant dose of 100 mg (administered as one 100 mg tablet) is the highest clinical dose of ubrogепant for which approval is being sought.
- A multiple-dose once daily administration of ubrogепant will provide a dosing regimen similar to the potential real-world use of ubrogепant in combination with migraine preventive MABs and is considered adequate to satisfy the objectives of the study.
- 140 mg erenumab and 240 mg galcanezumab are the highest approved doses of the CGRP receptor MAB (erenumab) and CGRP ligand MAB (galcanezumab), respectively.

4.4. End of Study Definition

The end of the study is defined as the date of the last visit (Follow-up) of the last participant in the study on Day 45 (± 3 days), or at early termination.

A participant is considered to have completed the study if he/she has not been terminated early and has completed all phases of the study through the last visit (Follow-up) on Day 45 ± 3 (30 [± 3] days after the last dose of study intervention).

■	[REDACTED]
■	[REDACTED]
■	[REDACTED]
■	[REDACTED]
■	[REDACTED]
■	[REDACTED]
■	[REDACTED]
■	[REDACTED]
■	[REDACTED]
■	[REDACTED]
■	[REDACTED]

5.3. Lifestyle Considerations

5.3.1. Meals and Dietary Restrictions

1. Water can be allowed as desired except for 1 hour before and after oral study intervention administration. Participants will be required to undergo a 10-hour overnight fast prior to dosing on Days 1, 12, 13, 14, and 15 and will maintain a fasted condition for an additional 4 hours following oral dose administration on these days. The oral study intervention will be administered with 240 mL of water. Following each dose administration, participants will continue their fast and remain seated upright and awake for 4 hours.
2. Participants will be served meals at appropriate times on admission days. On dosing days with study intervention administration (Days 1, 8, 12, 13, 14, and 15); no breakfast will be provided, but a standard lunch, dinner, and snack will be provided at approximately 4 hours postdose, 10 hours postdose, and 13 hours postdose, respectively. On all other days of confinement, breakfast, lunch, dinner, and snack will be served at approximately 0800, 1200, 1800, and 2100 hours, respectively.
3. Seville oranges, beverages or food containing quinine (bitter lemon, tonic water), poppy seeds, or taken dietary supplements or other foods or beverages that may affect various drug-metabolizing enzymes and transporters (eg, grapefruit, grapefruit juice, grapefruit-containing beverages), vegetables from the mustard green family (eg, kale, broccoli, watercress, collard greens, kohlrabi, brussel sprouts, mustard), or charbroiled meats must not be consumed within 14 days prior to dosing and throughout the duration of the study.
4. A copy of the menu with the total nutritional content (fat, protein, carbohydrates, and calories) of each component of each meal and snack will be made available to the sponsor at the start of the study. Participants will be instructed to consume the entire contents of each meal and snack, if possible. Study center personnel will document the percentage or the amount of consumed food for each participant.
5. While admitted in the study center, participants will be provided with standardized low-fat (< 20 g) meals.
6. Participants must refrain from implementing drastic changes in their diet or start a new diet during the study.

5.3.2. Caffeine, Alcohol, and Tobacco

1. Participants will abstain from ingesting caffeine- or xanthine-containing products (eg, coffee, tea, cola drinks, and chocolate) for at least 2 hours before dosing and at least 4 hours after dosing.
2. Alcohol intake should be limited to no more than 1 drink per day throughout the study. A drink is defined as a 12-ounce can/bottle of beer, a 4-ounce glass of wine, or 1 ounce of liquor.

3. Participants who use tobacco products will be instructed that use of nicotine-containing products (including nicotine patches) will not be permitted while they are in the clinical unit.

5.3.3. Activity

Maintaining a consistent lifestyle when participating in a clinical trial is vital. Participants will abstain from strenuous exercise or starting an intense exercise regimen for at least 7 days before blood collection for clinical laboratory tests on Day 1 and throughout the duration of the study, including the follow-up period. Participants may participate in light recreational activities during the study conduct (eg, watching television, reading).

5.4. Screen Failures

Individuals who do not meet the criteria for participation in this study (screen failures) may be rescreened unless the reason for screen failure was a positive urine drug screen. A participant who is rescreened will be assigned a new identification number and must sign the informed consent at the time of re-screening.

6. Study Intervention

Study intervention is defined as any investigational intervention(s), marketed product(s), or placebo intended to be administered to a study participant according to the study protocol.

6.1. Study Intervention(s) Administered

- Study Intervention A: Single oral 100-mg dose of ubrogapant tablet on Day 1
- Study Intervention B: Single SC injection of 140-mg erenumab on Day 8
- Study Intervention C: Two consecutive SC injections of 120-mg galcanezumab on Day 8
- Study Intervention D: Repeated once daily oral doses of 100-mg ubrogapant on Days 12, 13, 14, and 15

Migraine participants will be randomized to either Part 1 or 2 and will receive study interventions in a fixed sequence. Parts 1 and 2 could be conducted in parallel. In Part 1, 20 participants will receive a single oral dose of 100 mg ubrogapant alone (Study Intervention A) on Day 1, a single SC injection of 140 mg erenumab alone (Study Intervention B) on Day 8, followed by once daily oral doses of 100 mg ubrogapant on Days 12 through 15 (Study Intervention D) under fasted conditions. Similarly, in Part 2, a separate cohort of 20 participants will receive a single oral dose of 100 mg ubrogapant alone (Study Intervention A) on Day 1, 2 consecutive SC injection of 120 mg galcanezumab alone (Study Intervention C) on Day 8, followed by once daily oral doses of 100 mg ubrogapant on Days 12 through 15 (Study Intervention D) under fasted conditions. There will be a 7-day washout period between the administration of Study Intervention A and Study Intervention B (Part 1) or Study Intervention A and Study Intervention C (Part 2) and an 11-day washout period between ubrogapant doses.

Table 6-1 Study Interventions

Study Intervention Name	Ubrogепant (Intervention A)	Ubrogепant (Intervention D)	Aimovig (Erenumab) (Intervention B)	Emgality (galcanezumab) (Intervention C)
Dose Formulation	Tablet	Tablet	Solution for injection	Solution for injection
Identity of Formulation	100 mg ubrogепant	100 mg ubrogепant	140 mg/mL erenumab aooe	120 mg/mL galcanezumab gnlm
Device Configuration	NA	NA	Single-dose prefilled SureClick autoinjector [REDACTED] or single-dose prefilled syringe [REDACTED]	Single-dose prefilled pen [REDACTED] or single-dose prefilled syringe [REDACTED]
Route of Administration	Oral	Oral	Subcutaneous injection	Subcutaneous injection
Dosing Instructions	1 tablet to be administered with 240 mL of water, under fasted conditions on Day 1	1 tablet to be administered with 240 mL of water, under fasted conditions on Days 12, 13, 14, and 15	Single subcutaneous injection of 140-mg erenumab in the abdomen, thigh, or upper arm on Day 8	Two consecutive subcutaneous injections of 120-mg galcanezumab in the abdomen, thigh, back of the upper arm, or buttocks on Day 8
Packaging and Labeling	Study intervention will be provided in bottles, each containing 35 tablets. Each bottle will be labeled as required per country requirement.	Study intervention will be provided in bottles, each containing 35 tablets. Each bottle will be labeled as required per country requirement.	Study intervention will be provided as either single-dose prefilled SureClick autoinjector or single-dose prefilled syringe. Each autoinjector/pre-filled syringe will be labeled as required per country requirement.	Study intervention will be provided as either single-dose prefilled pen or single-dose prefilled syringe. Each pre-filled pen/pre-filled syringe will be labeled as required per country requirement.
Manufacturer	Allergan plc, Clonshaugh, Ireland	Allergan plc, Clonshaugh, Ireland	Amgen Inc, Thousand Oaks, CA	Eli Lilly and Company, Indianapolis, IN

6.2. Preparation/Handling/Storage/Accountability

1. The investigator or designee must confirm appropriate temperature conditions have been maintained during transit for all study intervention received and any discrepancies are reported and resolved before use of the study intervention.
2. Only participants enrolled in the study may receive study intervention, and only authorized site staff may supply or administer study intervention. All study intervention must be stored in a secure, environmentally controlled, and monitored (manual or automated) area in accordance with the labeled storage conditions with access limited to the investigator and authorized site staff.
3. The investigator, institution, or the head of the medical institution (where applicable) is responsible for study intervention accountability, reconciliation, and record maintenance (ie, receipt, reconciliation, and final disposition records).
4. All unused study intervention and empty kits and bottles must be returned to the sponsor at the termination of the study. Unit counts will be performed when the study intervention is returned, and all study intervention must be accounted for. Used syringes and pens should be discarded at the site.

6.3. Measures to Minimize Bias: Randomization and Blinding

Participants will be randomized to 1 of 2 parts: Part 1 or Part 2. Participants randomized to Part 1 will receive Study Intervention A on Day 1, Study Intervention B on Day 8, and Study Intervention D once daily on Days 12 through 15. Participants randomized to Part 2 will receive Study Intervention A on Day 1, Study Intervention C on Day 8, and Study Intervention D once daily on Days 12 through 15.

[REDACTED]

[REDACTED]

This is an open-label study; no blinding of assigned study intervention will occur.

6.4. Study Intervention Compliance

Participants will receive all doses under the direct supervision of study center personnel. Each participant's mouth and hands will be checked to ensure that the oral study interventions A and

D have been taken. Subcutaneous injections for study interventions B and C will be administered by site staff. Study intervention compliance will be assumed to be 100% when oral and subcutaneous dosing has been recorded in the eCRF.

Dosing should occur at the same time each dosing day for a participant; differences in dosing times > 60 minutes will be noted as protocol deviations, and the reason for deviation must be recorded in the source documents and eCRFs.

Galcanezumab injections should be administered consecutively with no more than 5 minutes between injections. A difference in injection times > 5 minutes will be noted as protocol deviations, and the reason for deviation must be recorded in the source documents and eCRFs.

The study center will keep an accurate drug disposition record that specifies the amount of study intervention administered to each participant and the date of administration.

6.5. Concomitant Therapy

[figure not shown]
Any medication or vaccine (including over-the-counter, prescription medicines, vitamins, herbal supplements, and/or cannabis or other specific categories of interest) that the participant is receiving at the time of enrollment or receives during the study must be recorded along with:

- Indication
- Dates of administration including start and end dates
- Dosage information including dose and frequency

At screening, upon admission to and discharge from the study center, EOD, and the Follow-up Visit, study center staff will question each participant specifically on the use of concomitant medications. Study center staff must notify the sponsor immediately if a participant consumes any concomitant medications not permitted by the protocol. Participants who admit to using prohibited concomitant medications may be discontinued from the study at the discretion of the investigator or the sponsor.

6.5.1. Prohibited Interventions and Washout Before the Study

Participants must discontinue any of the medications listed in the table below for the specified period prior to Day -1. These medications are prohibited for the duration of the study. Other stable medications being used at screening may be continued. A medication will be considered stable if the dose and frequency remain unchanged for at least 14 days prior to screening.

The investigator or sponsor reserves the right to exclude a participant from participation in the study if a medication taken 14 or more days before the study start may interfere with the study outcome (eg, a drug with prolonged half-life).

Any hormonal product taken within 30 days or any other medication taken within 14 days before the first dose of study intervention will be recorded in the eCRF as a prior medication.

The decision to administer a prohibited medication/intervention during the study period is done with the safety of the study participant as the primary consideration. When possible, the sponsor should be notified before the prohibited medication/intervention is administered.

6.5.2. Permitted Interventions

Therapy considered necessary for the participant's welfare may be given at the discretion of the investigator. If the permissibility of a specific concomitant medication or prior medication/intervention is in question, please contact the sponsor. All concomitant/prior medication use must be reviewed by the investigator in consultation with the sponsor prior to enrollment.

The following medications are allowed during the study, but are prohibited within 48 hours prior to taking oral study intervention:

- any triptan
- any ergot derivative
- any opioid
- any NSAID
- any other form of analgesic (including acetaminophen and Excedrin®)
- any antiemetic agent
- any proton pump inhibitor

The following medications are allowed during the study, but are prohibited within 24 hours prior to taking oral study intervention:

- any antacid
- any H2 blocker

Aspirin up to 325 mg/day is allowed for cardiac prophylaxis. Daily use of gabapentin/pregabalin is allowed.

Selective serotonin reuptake inhibitors (SSRI) or serotonin norepinephrine reuptake inhibitors (SNRI) will be permitted provided that treatment is stable at Screening and continues without change in dose throughout the study. SSRIs and SNRIs may not be started during the study.

For medications taken for migraine, all past and current medications will be recorded in the eCRF. Any medication taken during the study between the date of the first dose of study intervention and the date of the EOD visit will be recorded in the eCRF as a concomitant medication; any medication started after the EOD visit will not be considered a concomitant medication and should not be captured in the eCRF.

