In Phase 1 studies, single doses of 1 to 400 mg ubrogепant and multiple doses of ubrogепant up to 400 mg once daily (QD) for 10 consecutive days and 150 mg QD for 28 consecutive days have been evaluated. Ubrogепant was generally safe and well tolerated in these studies. In the multiple dose safety and tolerability studies evaluating hepatic effects of 150 mg QD for 28 days and high frequency, intermittent dosing of 100 mg (2 days ubrogепant followed by 2 days placebo) for 56 days, no signs of drug-induced liver injury (DILI) were observed based on a systematic measurement of serum ALT and aspartate aminotransferase (AST). The most frequently reported clinical AEs in these Phase 1 studies include nasopharyngitis, headache, and nausea. Adverse events have generally been transient and mild to moderate in intensity. Dose-proportional PK was noted in the dose range of 1 to 400 mg. Ubrogепant is rapidly absorbed with maximum plasma concentrations achieved in 0.5-1.5 hours. Ubrogепant is metabolized to an inactive metabolite almost exclusively by CYP3A4 with subsequent glucuronidation. Ubrogепant has a short terminal elimination half-life ($T_{1/2}$) of 5 to 7 hours with no accumulation after QD repeated dosing.

A Phase 2b clinical study was conducted, which compared 1-, 10-, 25-, 50-, and 100-mg doses of ubrogепant to placebo in the acute treatment of migraine. Overall, all the ubrogепant doses tested were well tolerated and the adverse event profile of all ubrogепant doses did not differ significantly from placebo. For the primary efficacy endpoint of pain freedom at 2 hours, ubrogепant doses of 1 and 10 mg did not differ from placebo, but doses of 25, 50, and 100 mg were better than placebo. For the primary efficacy endpoint of pain relief at 2 hours none of the ubrogепant doses differed from placebo, probably due to a high placebo response rate.

Further efficacy and safety of ubrogепant were established in 2 randomized, double-blind, placebo-controlled, single-attack, Phase 3 studies (UBR-MD-01 and UBR-MD-02). The results from these studies demonstrated that both ubrogепant 50 mg and 100 mg are superior to placebo in the acute treatment of migraine based on the coprimary efficacy endpoints (pain freedom and

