6.5.3. Rescue Medicine

The study site will supply rescue medication that will be obtained locally. Rescue medication includes medications for the acute treatment of migraine. The following rescue medications may be used: triptans, ergotamines, NSAIDs, acetaminophen or combination analgesics (ie Excedrin[®]), opioids, or other medications that are not explicitly prohibited and may be taken during the study. In the Screening period, rescue medication can be taken if headache of any severity develops.

Although the use of rescue medications is allowable at any time during the study, the use of rescue medications should be delayed, if possible, for at least 2 hours following the administration of study intervention. The date and time of rescue medication administration as well as the name and dosage regimen of the rescue medication must be recorded.

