## 5.6 Data Handling and Storage

A source data file from [REDACTED] will be transferred to Data Management via secure File Transfer Protocol (sFTP). Data Management will use the data for reconciliation against case report form (CRF) data and general cleaning.

Data Management shall provide the data file to Statistical Programming who will add the data to the [REDACTED] software for the calculation of PK parameters. Once the [REDACTED] is created, Statistical Programming will notify the Allergan Clinical Pharmacology representative via email and transfer it to the relevant group via a shared study-specific repository, in the [REDACTED].

Pharmacokinetic analysis and statistical analysis of pharmacokinetic data will be performed using [REDACTED] or other appropriate software.

Unless otherwise specified in subsequent sections, these general data handling instructions will be followed:

- All measured data will be used in analysis initially unless it may be excluded in accordance to regulatory guidances. Measured data not used and the reasons for its exclusion from the final analysis will be documented in the clinical study report (CSR).
- The actual sampling times will be used in the calculations of PK parameter values, nominal sample times will be used in the calculation of descriptive statistics.
- All postdose time points for which no sample is collected will be treated as missing. No value will be imputed for these missing values.
- Concentration data below the lower limit of quantitation (BLQ) will be defaulted to 0.00.

A data file (‘.xpt’ or ‘.xls’ format) containing PK parameter values will be generated by the Clinical Pharmacology representative and added to the shared study-specific repository for retrieval by Statistical Programming and for archival. If necessary, a document defining the content and CDISC parameter names will also be provided. Other files necessary to reproduce the analysis of PK parameter values, e.g., the WinNonlin Project file, will be archived in PKS or another appropriate study-specific repository.

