## **7.2 Statistical Analysis**

Plasma PK parameters ( $C_{max}$ ,  $AUC_{0-t}$ , and  $AUC_{0-\infty}$ ) for ubrogepant will be compared using a linear mixed-effects model with study intervention as fixed effect and participant as a random effect in each part of the study for the PK1 population. Statistical analysis will be based on log-transformed values for the  $C_{max}$  and AUC parameters of ubrogepant. For each study part, the 2-sided 90% CI will be constructed for the ratio of least squares geometric means of  $C_{max}$ ,  $AUC_{0-t}$ , and  $AUC_{0-\infty}$  of ubrogepant in combination with CGRP MAB (Test, Day 12) versus ubrogepant alone (Reference, Day 1). No effect of co-administration with CGRP MABs on the PK of ubrogepant will be concluded if the 90% CIs for the ratios of ubrogepant PK parameters for test study intervention versus reference study intervention are within the limits of 80% to 125%.

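### Section 6.5.2 bars acid-reducing drugs after dosing in the Day 12 test profile but not in the Day 1 reference profile, and it conflicts with Section 6.5.3 on rescue drugs

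*Protocol*

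**What the plan says.** Protocol Section 6.5.2 has two lists. For triptans, ergots, opioids, NSAIDs, other analgesics, antiemetics and proton pump inhibitors it says "The following medications are allowed during the study, but are prohibited within 48 hours prior to taking oral study intervention". For antacids and H2 blockers it says "The following medications are allowed during the study, but are prohibited within 24 hours prior to taking oral study intervention". Neither list has a post-dose window. The same section lets the investigator give therapy needed for the participant's welfare.

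Section 6.5.3 places no time limit on rescue use during the study. It names triptans, ergotamines, NSAIDs, acetaminophen or combination analgesics and opioids, and adds other drugs that are not explicitly prohibited. Its only timing request is that "the use of rescue medications should be delayed, if possible, for at least 2 hours following the administration of study intervention".

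Oral ubrogepant is given once on Day 1 and then, per Section 6.3, as "Study Intervention D once daily on Days 12 through 15". Plasma is sampled from 0 to 24 h after the Day 1 and Day 12 doses (Section 8.5.1). Section 2.2 states that ubrogepant "is rapidly absorbed with maximum plasma concentrations achieved in 0.5-1.5 hours".

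SAP Section 7.2 compares ubrogepant "in combination with CGRP MAB (Test, Day 12) versus" ubrogepant alone on Day 1. Study intervention is the only fixed effect, participant is a random effect, and the 90% CI is judged against 80% to 125%. SAP Section 5.6 says "All measured data will be used in analysis initially unless it may be excluded in accordance to regulatory guidances" and asks that exclusions be documented in the study report. For concomitant drugs in general, the timing item in Protocol Section 6.5 is "Dates of administration including start and end dates"; Section 6.5.3 asks for date and time, but for rescue drugs only.

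**The concern.** A fixed-sequence ratio attributes every systematic difference between Day 12 and Day 1 to the antibody. The conditions on the two profile days should therefore match in everything the protocol controls. Here they do not. The look-back rule protects the period before each dose equally, but because Day 12 is followed by another dose the next day and Day 1 is not, it also shields the post-dose profile on the test side alone. No visible passage gives a reason; it looks like a by-product of comparing a single dose with the first of four daily doses.

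The difference can arise without a migraine attack. Section 6.5.1 lets stable medication continue. A regular user of a proton pump inhibitor, H2 blocker or antacid must stop before the Day 1 dose, may resume straight after it as Section 6.5.2 is written, and may not do so after the Day 12 dose. The fasting and water rules in Section 5.3.1 do not mention medication. By restricting these drugs before a dose, the protocol itself treats them as able to interfere. If post-dose use changed Day 1 Cmax or AUC, the model could not tell that change from an antibody effect, and it could either mimic or hide one.

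**Working it through.** **Inputs.** Oral doses on Days 1, 12, 13, 14 and 15; look-back windows of 48 h and 24 h (Section 6.5.2); profiles of 0-24 h after the Day 1 and Day 12 doses (Section 8.5.1); dosing-time tolerance of 60 minutes (Section 6.4); time to peak 0.5-1.5 h and half-life 5-7 h (Section 2.2).

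**Plan's own figure.** Day 12 minus Day 1 is 11 days (264 h), which agrees with the 11-day washout in Section 6.1.

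**Coverage by Section 6.5.2 alone.** Let T be the time of the Day 12 dose.

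| Profile | 48-hour list | 24-hour list |
|---|---|---|
| Day 1, 0-24 h | next window opens at 264 - 48 = 216 h: covers 0 of 24 h | next window opens at 264 - 24 = 240 h: covers 0 of 24 h |
| Day 12, Day 13 dose on time | window T-24 to T+24: covers 24 of 24 h | window T to T+24: covers 24 of 24 h |
| Day 12, Day 13 dose 60 min late | window T-23 to T+25: covers 24 of 24 h | window T+1 to T+25: covers 23 of 24 h = 95.8% |

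**Adding Section 6.5.3.** The named rescue classes are permitted after either dose, with the same request for a 2-hour delay. For these classes the text contradicts itself on Day 12: Section 6.5.2 bars them because a Day 13 dose follows, and Section 6.5.3 allows them. The clear asymmetry is left for antacids, H2 blockers and proton pump inhibitors. Antiemetics depend on whether they count as rescue.

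**When use could matter.** Assume a one-compartment model with the stated time to peak and half-life. Solving ln(ka/k)/(ka - k) = Tmax with k = ln 2/half-life gives ka of 1.88 to 9.15 per hour. The fraction absorbed by 2 h, 1 - exp(-2ka), is 97.6% to 100%. A drug taken later than about 1.5-2 h can therefore do little to Cmax or absorption. The share of AUC still to come after 2 h is 77.1% to 85.9%, so an effect on clearance could still act on AUC.

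**Possible size (assumptions, not figures from the documents).** If a fraction p of participants take a drug after the Day 1 dose only, and it multiplies their Day 1 exposure by (1 + x), the Day 12/Day 1 geometric mean ratio becomes (1 + x)^(-p):

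| p | x = -20% | x = +20% |
|---|---|---|
| 5% | 101.1% | 99.1% |
| 10% | 102.3% | 98.2% |
| 25% | 105.7% | 95.5% |

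A second view uses migraine onset within 1.5 h of dosing as a stand-in for use early enough to change Cmax. With an assumed 2 to 8 attacks per 30 days, the expected number among 20 participants is 20 x [1 - exp(-(a/30)(1.5/24))], which is 0.08 for a = 2 and 0.33 for a = 8. If each had Day 1 Cmax multiplied by an assumed 0.7, the upper value shifts the ratio by 0.7^(-0.33/20) = 1.006, about 0.6%.

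**The case against.** The strongest reply is that most of the listed drugs are not subject to a clear Day 12 ban. Section 6.5.3 allows the rescue classes on both profile days, the 2-hour request is the same on both, and the welfare clause applies on both. That stands: for those classes the finding is a contradiction to be reconciled, not a one-sided restriction. A reader might infer from Section 6.5.2 alone that the whole list is banned throughout Day 12 and free throughout Day 1. Taken together, the two sections do not support that.

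A second reply is that the restrictions most relevant to absorption, those before dosing, already match, and that participants are fasted and confined until 24 h after the Day 1 dose (Section 8). This also stands, and it makes early use unlikely, although neither fact bars it.

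A third reply concerns size. A reader might count every attack over the full 24 h, about 1.3 to 4.7 of 20 participants at the assumed 2 to 8 attacks per 30 days, apply the result to Cmax and conclude that the CI could leave 80% to 125%. The documents do not support this. Cmax is reached by 1.5 h, attacks lead mainly to rescue drugs that are permitted on both days, and attack frequency says nothing about use of acid-reducing drugs.

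Nor does the SAP retain every profile regardless: Section 5.6 allows documented exclusions. But it gives no criterion for concomitant-drug use, the PK1 definition does not mention it, and Section 7.2 has no sensitivity analysis. Finally, Table 6-2, the table in Section 6.5.1, the schedule of activities and the day-by-day schedule in Appendix 8 are not visible in the public text and could add limits; the case report form might also collect times.

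**Conclusion.** The point holds in a limited form and is minor. For antacids, H2 blockers and proton pump inhibitors, and for antiemetics unless counted as rescue, the visible text bars post-dose use through essentially the whole Day 12 profile and leaves it unrestricted on Day 1. For triptans, ergots, NSAIDs, analgesics and opioids, Sections 6.5.2 and 6.5.3 conflict on Day 12.

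The coverage figures follow from the dosing calendar and need no assumption beyond the 60-minute tolerance. The effect on the primary ratio cannot be estimated, because the documents give neither an interaction size nor a usage rate for any listed drug. Under the assumed ranges shown, the ratio moves to between 95.5% and 105.7%. For Cmax the effect is probably small, since only use before about 1.5-2 h matters; AUC has a longer exposed period, but only if a drug alters clearance. These figures describe possible size, not expected bias, and they do not show that the no-effect conclusion is at risk. A reader might extend the point to the CGRP samples or the interim vital signs; the documents offer nothing to size that, and no such claim is made here.

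**What to change.** 1. Reconcile Protocol Sections 6.5.2 and 6.5.3 so that the same concomitant-drug conditions apply over 0-24 h after the Day 1 dose and after the Day 12 dose. Which conditions is for the sponsor to decide; the comparison needs only that they match.
2. Record the clock time of any drug listed in Section 6.5.2 taken on Days 1-2 and 12-13, as Section 6.5.3 already requires for rescue drugs.
3. In SAP Section 7.2, flag profiles with listed-drug use 0-24 h after the Day 1 or Day 12 dose, and add a sensitivity analysis of the Cmax and AUC ratios without those participants.

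The cost is a short protocol clarification, one data field collected around confinement that is already planned, and one extra model run. The sensitivity set will be slightly smaller than the main set, so its CI will tend to be somewhat wider.
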